**7.7.2 Treatment Effects on Failure by 36 Months by Subgroup**

This study has liberal inclusion/exclusion criteria. It is possible that the treatment effect is not consistent across different subgroups of the population. With potentially small numbers of participants in subgroups, results of subgroup analyses will be interpreted with caution and the interpretation may depend on whether the primary analysis demonstrates a significant overall treatment group difference.

The subgroup analyses will be performed by modifying the primary analysis to adjust for the subgroup factor and an interaction between the subgroup factor and treatment group.

Baseline subgroups of interest are:

1. Duration of ET prior to enrollment: <6 months vs.  $\geq$  6 months
2. Stereoacuity
  - a. Distance Randot Stereotest: nil vs. not nil
  - b. Near RPS Test through +3.00 D lenses: nil vs. not nil
3. Intermittent ET (or esophoria) vs. constant ET
4. Motor response at near to +3.00 D trial frames testing classified as follows:
  - a. No response (tropia  $\geq$ 10 $\Delta$  by SPCT)
  - b. Microtropia ( $<10\Delta$ )
  - c. Phoria or orthophoria
5. Near stereoacuity response vs. no near stereo response through +3.00 D trial frames
  - a. Stereoacuity response is defined as near stereoacuity improvement of at least 2 levels (for participants who have stereoacuity in SVLs) or presence (any level) of near stereoacuity in +3.00 D lenses (for participants who do not have stereoacuity in SVLs).
  - b. Participants who have 48" or 72" of near stereopsis in SVLs cannot meet the stereoacuity response criteria and will be excluded from this subgroup analysis
6. Gradient AC/A ratio
  - a. By tertiles
  - b.  $<2.5$  vs. 2.5 to 6 vs.  $>6$
7. Age: 3 to <6 years vs. 6 to <9 years

The proportion of participants that fall into each of the subgroups is unknown. Table 5 shows the expected half-width of the 95% CI for the treatment group difference in the primary outcome in subgroups of various sizes. For example, if the observed proportions of failure by 36 months are 5% with SVLs and 15% with BFLs in a subgroup with 100 participants per treatment group, the expected half-width of the 95% CI for the treatment group difference would be 8%.

1299 **Table 5. Expected half-width of 95% CI\* for treatment group difference in the proportion**  
 1300 **of failures by 36 months in subgroups with various sizes**

Observed % of Failure in SVL Group (p1)	Observed % of Failure in BFL Group (p2)	Observed Treatment Difference in % of Failure (p2 – p1)	Number Per Treatment Group in Subgroup							
			25	50	75	100	125	150	175	200
5%	5%	0%	12%	9%	7%	6%	5%	5%	5%	4%
5%	10%	5%	15%	10%	8%	7%	7%	6%	5%	5%
5%	15%	10%	16%	12%	9%	8%	7%	7%	6%	6%
5%	20%	15%	18%	13%	10%	9%	8%	7%	7%	6%
5%	25%	20%	19%	13%	11%	10%	8%	8%	7%	7%
10%	10%	0%	17%	12%	10%	8%	7%	7%	6%	6%
10%	15%	5%	18%	13%	11%	9%	8%	7%	7%	6%
10%	20%	10%	20%	14%	11%	10%	9%	8%	7%	7%
10%	25%	15%	21%	15%	12%	10%	9%	8%	8%	7%
10%	30%	20%	21%	15%	12%	11%	10%	9%	8%	8%
15%	15%	0%	20%	14%	11%	10%	9%	8%	7%	7%
15%	20%	5%	21%	15%	12%	11%	9%	9%	8%	7%
15%	25%	10%	22%	16%	13%	11%	10%	9%	8%	8%
15%	30%	15%	23%	16%	13%	11%	10%	9%	9%	8%
15%	35%	20%	23%	17%	13%	12%	10%	10%	9%	8%

1301 \*Half-width of a 2-sided 95% CI =  $1.96 \times \sqrt{p1*(1-p1)/n1 + p2*(1-p2)/n2}$

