### 193 **1.9 Study Objectives**

- 194 1. To compare the proportion of participants with failure by 36 months between BFL and  
195 SVL groups (failure = worsening of distance ET, reduction in near stereoacuity, frequent  
196 diplopia (“more than 2 times per day” over the last week), or undergoing non-study  
197 treatment)
- 198 2. To compare binocular function scores in BFLs 2 months following failure or at 38  
199 months if no failure (whichever comes first) between the BFL and SVL spectacles groups
- 200 3. To compare the proportion of participants with failure by 36 months between BFL and  
201 SVL groups according to baseline factor subgroups of: pre-enrollment duration of  
202 constant ET, presence of near stereoacuity on the Randot Preschool Stereoacuity test, in-  
203 office response of near motor alignment to +3.00 D lenses, and gradient AC/A ratio

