### 1151 7.3 Sample Size

1152 Sample size estimation is based on data from the retrospective cohort study conducted by  
1153 Whitman et al. After approximately 4 years of follow-up, 15.6% of the BFL group and 3.9% of

1154 the SVL group underwent strabismus surgery, all of whom had an increase in the distance angle  
 1155 of deviation to more than  $10\Delta$  by PACT (average increase from baseline was  $25\Delta$  in the BFL  
 1156 group and  $20.5\Delta$  in the SVL group). In the current study, the primary outcome is based on  
 1157 distance motor failure (based on SPCT), near stereoacuity failure, or diplopia “more than 2 times  
 1158 per day” over the last week by 36 months. Given a shorter follow-up, the proportion of distance  
 1159 motor failures may be less than that found in the Whitman et al. study. The proportion of near  
 1160 stereoacuity failures is believed to be less in the BFL group than the SVL group, but no data are  
 1161 available to provide estimates of the failure proportion for each group.  
 1162

1163 Table 4 shows the sample size estimates under various assumptions for the primary outcome in  
 1164 the SVL group and the difference in the primary outcome between the BFL and SVL groups. To  
 1165 be conservative, the total sample size needed to detect a treatment group difference is calculated  
 1166 using a two-sided Pearson chi-square test with a type I error rate of 5% and 90% power. Power is  
 1167 expected to increase slightly using a time-to-event approach for the primary outcome analysis.  
 1168

1169 **Table 4. Total sample size needed to detect a treatment group difference in proportions of  
 1170 failure by 36 months under various assumptions**

% of Failure in SVL Group	Treatment Group Difference in % of Failures (BFL – SVL)							
	5%	6%	7%	8%	9%	10%	15%	20%
3%	870	656	518	424	356	306	172	116
4%	1018	756	592	480	400	342	186	124
5%	1164	856	664	534	442	376	202	130
6%	1304	954	734	588	484	408	214	138
7%	1442	1140	802	640	524	440	228	146
8%	1576	1140	870	690	564	472	242	152
9%	1708	1230	936	740	602	502	254	158
10%	1836	1318	998	788	640	532	266	164
11%	1960	1402	1060	834	676	562	278	172
12%	2082	1486	1120	880	712	590	290	178
13%	2198	1566	1178	924	746	618	302	182
14%	2314	1644	1236	966	780	644	312	188
15%	2424	1720	1290	1008	812	670	322	194

1171  

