 1172 Assuming a failure probability of 5% in the SVL group and 15% in the BFL group, a sample size  
 1173 of 376 (188 per group) provides 90% power to detect a treatment group difference with a two-  
 1174 sided type I error rate of 5%. The total sample size is increased to 444 (222 per group) to account  
 1175 for up to a 15% loss to follow-up over 36 months.

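### Section 7.7.2 tests the treatment interaction with gradient AC/A ratio and with age only in classes; a continuous term, with the classes kept for display, would use the roughly 38 expected failures better if the effect is graded

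*Protocol*

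**What the plan says.** Section 7.7.2 builds each subgroup analysis by adding the subgroup factor and its interaction with treatment to the primary analysis, which section 7.6 defines as a covariate-adjusted Cox model. The same section then fixes the coding of each factor.

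- Item 6, gradient AC/A ratio, has two codings: tertiles, and three fixed classes (below 2.5, 2.5 to 6, above 6). Neither is named as the main one.
- Item 7, age, has one coding: "Age: 3 to <6 years vs. 6 to <9 years".

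No continuous interaction is stated for either factor. Section 7.7.2 adds the caveat "With potentially small numbers of participants in subgroups, results of subgroup analyses will be interpreted with caution", and Table 5 gives the expected precision of the treatment difference within subgroups. No power is stated for any interaction.

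Objective 3 in section 1.9 asks for the comparison of failure by baseline subgroups. Its list of factors ends with "office response of near motor alignment to +3.00 D lenses, and gradient AC/A ratio". Age is not on that list, nor in the matching objective of the Protocol Summary.

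On numbers, section 7.3 states: "Assuming a failure probability of 5% in the SVL group and 15% in the BFL group, a sample size" "of 376 (188 per group) provides 90% power to detect a treatment group difference with a two"-sided 5% test, with the total raised to 444 (222 per group) for up to 15% loss.

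**The concern.** AC/A ratio and age are measured on continuous scales. Putting them into classes discards the differences between children in the same class. For AC/A it also spends two degrees of freedom where a linear interaction needs one. With few failures, that information is costly to lose.

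AC/A raises a second problem. Two three-class codings of one factor can give different answers, and the protocol does not say which one serves Objective 3. A single continuous interaction would give one answer.

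At stake is how well the trial can show that the balance between lens types shifts with AC/A ratio or with age. The primary comparison is not affected.

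**Working it through.** **Inputs from the protocol (sections 7.3 and 7.7.2).** Failure by 36 months of 5% (SVL) and 15% (BFL); 188 evaluable and 222 randomised per group; 15% loss; two-sided 5% level; the codings above.

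**Assumptions, because the protocol gives no figure.** Age uniform from 3 to 9 years; AC/A roughly normal; treatment hazard ratio changing log-linearly with the factor, by a ratio r per SD.

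**The plan's own figure.** With pooled proportion 0.10:

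n = [1.96·√(2·0.10·0.90) + 1.2816·√(0.05·0.95 + 0.15·0.85)]² / 0.10² = 187.05, so 188 per group and 376 in total. Then 188/0.85 = 221.2, so 222 per group and 444 in total. Both figures reproduce.

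**Expected failures.** SVL 188 × 0.05 = 9.4; BFL 188 × 0.15 = 28.2; total 37.6. Per AC/A tertile: 9.4/3 ≈ 3.1 SVL and 28.2/3 = 9.4 BFL. With all 444 fully followed the total would be 222 × 0.20 = 44.4.

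**Precision of the continuous interaction.** The standard error of the log ratio of hazard ratios per SD is approximately √(1/9.4 + 1/28.2) = 0.377, and the noncentrality is λ = (ln r / 0.377)².

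**Information kept by the classes.** This is the share of the factor's variance lying between classes. For uniform age halved at 6 it is 0.75; for a normal factor in tertiles it is 0.793. Power comes from the noncentral chi-square: λ on 1 df (continuous), 0.75λ on 1 df (two age bands), 0.793λ on 2 df (tertiles).

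| r per SD | Continuous | Age, two bands | Loss (points) | AC/A tertiles | Loss (points) |
|---|---|---|---|---|---|
| 1.25 | 9% | 8% | 1 | 7% | 2 |
| 1.5 | 19% | 15% | 4 | 13% | 6 |
| 2.0 | 45% | 36% | 10 | 29% | 16 |
| 2.5 | 68% | 56% | 12 | 48% | 20 |
| 3.0 | 83% | 71% | 12 | 64% | 19 |

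Losses are taken before rounding.

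**Check by simulation.** Logistic likelihood-ratio tests with 188 per group and 1,500 runs per setting, for odds-ratio changes of about 1.5 to 3.7 fold per SD, gave losses of 4 to 13 points for age and 4 to 19 for AC/A tertiles. At about 2 fold, age gave 45% continuous against 37% in bands; AC/A gave 43% against 31%.

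**Other covariate distributions.** If ages are symmetric but less spread than uniform, or skewed to younger children, the share kept by the split at 6 falls to between 0.61 and 0.70. For the fixed AC/A cuts, several assumed normal distributions give 0.67 to 0.79.

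**The opposite shape.** Let the hazard ratio step by a factor R exactly at a class boundary. For AC/A the step is at the top tertile: indicator variance 2/9, squared correlation with the continuous factor 0.595. For age it is at 6 years: variance 1/4, squared correlation 0.75.

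| R | AC/A continuous | AC/A tertiles | Age continuous | Age two bands |
|---|---|---|---|---|
| 3 | 19% | 22% | 24% | 31% |
| 4 | 27% | 32% | 36% | 45% |
| 6 | 41% | 51% | 54% | 66% |

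Here the classes gain about 3 to 12 points.

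**Size needed for 80% power.** With the continuous term, r = exp[(1.96 + 0.84) × 0.377] ≈ 2.9 per SD.

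**The case against.** The strongest case for the plan is that Objective 3 asks about subgroups, and classes answer it as worded. The protocol claims no interaction power, plans precision within subgroups through Table 5, and promises caution. Its background describes sub-types by presence or absence of a high AC/A ratio, which fits a threshold view, and under a true threshold the classes do better. A supplementary continuous analysis could also stand in an analysis plan that is not shown.

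Much of this stands. The classes are not an error, they should be kept, and the direction of the loss depends on the shape of the effect. It does not remove the point. Section 7.7.2 does fix the coding, it leaves AC/A with two codings and no main one, and caution in interpretation does not recover discarded information. The step comparison also places the threshold exactly on a class boundary, the case most favourable to classes.

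A reader might infer four stronger things that the protocol does not support:

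- **That both factors belong to Objective 3.** Only AC/A does.
- **That a graded relation is expected.** The protocol nowhere says so.
- **That the three-class test has an inflated false-positive rate because failures are sparse.** That would need a simulation of the planned covariate-adjusted Cox model, which this check does not include.
- **That a continuous term would make the interaction well powered.** A ratio near 2.9 per SD is still needed for 80%.

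**Conclusion.** The point holds as an inexpensive improvement to a stated method, not as a flaw in the primary analysis. For a log-linear interaction of 1.5 to 3 fold per SD, with uniform age, roughly normal AC/A and 37.6 failures, class-only testing loses about 4 to 12 points of power for age and 6 to 20 for AC/A tertiles. The loss shrinks to 1 to 2 points for a weak interaction and reverses for a step at a class boundary. The protocol supplies neither the size nor the shape of the interaction, so these figures are conditional. Whichever coding is used, interaction power is low unless the effect is large, and the findings stay exploratory.

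The missing choice between the two AC/A codings holds whatever the shape of the effect.

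**What to change.** In section 7.7.2, items 6 and 7, state that the main treatment-by-factor interaction for gradient AC/A ratio and for age is estimated with the factor continuous in the Cox model. Functional form would be checked as section 7.6 already requires, with a low-order spline if linearity fails. Keep the tertiles, the fixed AC/A classes and the two age bands to display failure proportions and treatment differences, and as a supplementary look for threshold effects.

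The cost is a sentence or two of text and two extra model fits on data already to be collected. The downside is the assumed shape, which can be checked and which the retained classes help to guard against. Stating it before outcomes are known keeps the continuous analysis from being post hoc.

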## 1303 **7.8 Exploratory Analysis of Tertiary Outcomes**

1304 All tertiary outcomes will be considered exploratory. Point estimates and 95% CIs for treatment  
 1305 group differences will be reported (where applicable) with no adjustment for multiplicity.  
 1306 Binocularity and stereoacuity outcomes that are better suited to non-parametric methods will be  
 1307 described using the median and interquartile range for each treatment group.

### 1308 **7.8.1 Ocular Alignment at Distance and Near**

#### 1309 **7.8.1.1 Comparison of Randomized Treatments at 36 Months or Confirmed Failure**

1310 At the time of the primary outcome (36 months or confirmed failure), the magnitude of deviation  
 1311 by PACT and the change from baseline will be tabulated and described with summary statistics  
 1312 for each treatment group. The treatment group difference in the magnitude of deviation and the  
 1313 95% CI will be estimated using an analysis of covariance (ANCOVA) adjusting for the baseline  
 1314 PACT magnitude.

1315 The magnitude of deviation by SPCT and the change from baseline will also be tabulated and  
 1316 described with summary statistics for each treatment group. The proportions with constant ET of  
 1317  $\geq 10\Delta$ , constant ET of  $< 10\Delta$ , intermittent ET, esophoria, and orthophoria will be tabulated by  
 1318 treatment group.

1319 The above analyses will be performed separately for distance and near deviations as measured  
1320 through distance correction, to assess the magnitude of the underlying angle of deviation. In  
1321 addition, the near deviations as measured through OFFICE spectacles (i.e., SVLs with  
1322 cycloplegic refraction and +3.00 D power) will be analyzed similarly, to assess the impact of  
1323 +3.00 D lenses on the near deviation.

1324 **7.8.2 Binocular Function Test Score**

1325 **7.8.2.1 Subgroup Analysis of Secondary Outcome Binocular Function Score**

1326 The secondary outcome of binocular function test score in BFLs at the Secondary Outcome Visit  
1327 (Post-failure Secondary Outcome visit if failed or 38-month Secondary Outcome Visit if not  
1328 failed) as defined in section 7.7.1 will be further evaluated in subgroups specified in section  
1329 7.7.2.

1330 **7.8.2.2 Comparison of Overall Treatment Strategies at 38 Months**

1331 To evaluate real-world effectiveness of the overall treatment strategies the binocular function test  
1332 score at the 38-month Secondary Outcome Visit and the change from baseline will be tabulated  
1333 by treatment group. Distinct from the secondary outcome binocular function score (sections 7.7  
1334 and 7.8.2.1), this analysis will utilize the 38-month data for all participants, regardless of whether  
1335 they met failure criteria at a prior visit. Scores will be calculated using the same algorithm as  
1336 described in section 7.7.1 for combining the results of the RPS, Random Dot Butterfly, and W4S  
1337 tests that are measured through the bottom of the HOME spectacles for most participants (see  
1338 section 3.8 for exceptions). Results of the individual tests will also be tabulated separately for  
1339 each treatment group.

1340 **7.8.2.3 Comparison of Randomized Treatments at 36 Months or Confirmed Failure**

1341 The binocular function score will be evaluated at the primary outcome (36 months or prior  
1342 failure) (before the BFLs are prescribed) and compared between the SVL group and the BFL  
1343 group. At these visits, the best of two near stereoacuity measures by the RPS test in OFFICE  
1344 spectacles will be used when calculating the binocular function score. The binocular function  
1345 score at the time of treatment failure (if failed) or the 36-month Primary Outcome Visit (if not  
1346 failed) and the change from baseline will be tabulated by treatment group.

1347 **7.8.3 Near Stereoacuity**

1348 At baseline, near RPS stereoacuity measured in +3.00 D trial frames will be used for analysis. At  
1349 regular follow-up visits between 3 months and 36 months, the best of the two RPS measures in  
1350 OFFICE spectacles will be used for analysis.

1351 **7.8.3.1 Comparison of Randomized Treatments at the Secondary Outcome Visit**

1352 Near stereoacuity measured using the bottom portion of the participants' BFLs at the Secondary  
1353 Outcome Visit (Post-failure Secondary Outcome visit if failed or 38-month Secondary Outcome  
1354 Visit if not failed) and the change from baseline will be tabulated for each treatment group.

1355 **7.8.3.2 Comparison of Overall Treatment Strategies at 38 Months**

1356 To evaluate real-world effectiveness of the overall treatment strategies, near RPS stereoacuity at  
1357 the 38-month Secondary Outcome Visit and the change from baseline will be tabulated for each  
1358 treatment group, regardless of whether failure criteria were met at a prior visit. The analysis will

1359 use the same RPS stereoacuity measurement (in arcsec) that is taken through the bottom of the  
1360 HOME spectacles for most participants (see section 3.8 for exceptions).

1361 **7.8.3.3 Comparison of Randomized Treatments at 36 Months or Confirmed Failure**

1362 Near RPS stereoacuity at the time of the primary outcome (36 months or prior failure) and the  
1363 change from baseline will be tabulated for each treatment group.

1364 **7.8.4 Distance Stereoacuity**

1365 Scores from the Distance Randot Stereotest will be collected at enrollment, at 36 months using  
1366 the top portion of the HOME spectacles, and at 38 months using the top portion of the BFLs.  
1367 Distance stereoacuity will also be measured if a failure criterion is met before the 36-month visit.

1368 **7.8.4.1 Comparison of Randomized Treatments at the Secondary Outcome Visit**

1369 The Distance Randot Stereotest measured in BFLs at the Secondary Outcome Visit (Post-failure  
1370 Secondary Outcome visit if failed or 38-month Secondary Outcome Visit if not failed) and the  
1371 change from baseline will be tabulated for each treatment group.

1372 **7.8.4.2 Comparison of Overall Treatment Strategies at 38 Months**

1373 To evaluate real-world effectiveness of the overall treatment strategies, distance stereoacuity at  
1374 the 38-month Secondary Outcome Visit and the change from baseline will be tabulated for each  
1375 treatment group, regardless of whether failure criteria were met at a prior visit.

1376 **7.8.4.3 Comparison of Randomized Treatment at 36 Months or Confirmed Failure**

1377 The Distance Randot Stereotest measured at the time of the primary outcome (36 months or  
1378 confirmed failure) and the change from baseline will be tabulated for each treatment group using  
1379 the participant's HOME spectacles.

1380 **7.8.5 Short-term Effect of BFLs in SVL Group Post-failure and at 38 Months**

1381 In the SVL group, the changes in near RPS stereoacuity, distance stereoacuity, and the binocular  
1382 function test score from the time of the primary outcome (36 months or confirmed failure) to the  
1383 Secondary Outcome Visit (Post-failure Secondary Outcome visit if failed or 38-month  
1384 Secondary Outcome Visit if not failed) will be tabulated and described with summary statistics to  
1385 evaluate the short-term effect of BFL wear.

1386

1387 **7.9 Safety Analyses**

1388 **7.9.1 Distance Motor and Near Stereoacuity Treatment Failures**

1389 The occurrences of distance motor failure and near stereoacuity failure, as each is defined under  
1390 "treatment failure" (section 7.2) will be tabulated for each treatment group as safety outcomes.

1391 The risk of undergoing strabismus surgery is not included as a safety outcome given that surgery  
1392 is at the discretion of the investigator provided failure criteria have been met, with biases  
1393 expected to vary considerably among investigators.

1394 **7.9.2 Diplopia**

1395 Any new cases of diplopia will be tabulated for each treatment group. In addition, diplopia  
1396 occurring "more than 2 times per day" over the last week will also be tabulated for each  
1397 treatment group.

1398 **7.9.3 Reduction of Distance Visual Acuity**  
1399 Any cases of inter-ocular difference not within 0.2 logMAR and reduced visual acuity in best  
1400 refractive correction ( $\geq 0.2$  logMAR) in either eye will be tabulated by treatment group.

1401 **7.10 Spectacle Adherence**  
1402 Spectacle adherence assessed by a parental estimate at the start of each visit will be tabulated  
1403 over time for each treatment group over the 36 months in the study. Separately, spectacle  
1404 adherence for each treatment group will be tabulated for the 36- to 38-month window for non-  
1405 failures, and for the time window from prior treatment failure (i.e., Failure Confirmation Visit, if  
1406 required; otherwise, from the failure visit) to the Post-failure Secondary Outcome Visit if failed.

1407 **7.11 Additional Tabulations and Analyses**  
1408 The following tabulations and analyses will be performed:  
1409 • A flow chart accounting for all participants according to treatment group for all visits  
1410 • Visit completion rates for each follow-up visit according to treatment group  
1411 • Baseline demographics and clinical characteristics overall and by treatment group at  
1412 randomization  
1413 • Protocol deviations according to treatment group  
1414 • Number of and reasons for non-study treatment according to treatment group  
1415

1416

